	
 • We will collect cognitive, language, and motor scores from the Bayley Scales of Infant and Toddler Development- Third Edition (Bayley-III)⁵⁵ at 18-24 months of age to assess developmental delay. We will also include available data on the following outcomes at 18-24 months: cerebral palsy (using the Gross Motor Function Classification System), hearing impairment requiring hearing aids, and blindness. 	
Epigenetics	
 • CpG methylation signatures 	Exploratory aim to examine feasibility of evaluating differential methylation in genes encoding for cytochrome P450 enzymes involved in caffeine metabolism.

4 STUDY DESIGN

4.1 Overall Design

This is a phase I, open-label, dose-escalating PK and safety study of caffeine in neonates with HIE undergoing therapeutic hypothermia. There will be two cohorts, with two caffeine dosing regimens (see **Section 6.1.2, Dosing and Administration**). Each cohort will consist of 9 neonates and the intervention duration will be 48 hours. An interim safety analysis will be conducted following the follow-up period in the final cohort 1 participant (see **Section 9.4.4, Safety Analyses**) to assess for safety prior to enrollment in cohort 2. We hypothesize that drug clearance will be $\geq 20\%$ lower than expected for gestational age and birth weight and that the incidence of adverse events will be similar to those in published trials of therapeutic hypothermia.

4.2 Scientific Rationale for Study Design

The PK and safety of caffeine in the setting of HIE are unknown. Given that ischemic injury to the liver and kidneys and therapeutic hypothermia likely alters the metabolism and elimination (i.e., PK) of caffeine, a phase I study is essential to determine optimal dosing for larger, randomized controlled trials to investigate caffeine as a therapeutic agent to reduce NDI associated with HIE. This study will provide the necessary first step to design a larger phase trial to evaluate the safety and preliminary effectiveness of caffeine in reducing brain injury in neonates with HIE.

4.3 Justification for Dose

The two dosing regimens are based on available preclinical data in animals which suggest that methylxanthine doses of 20 mg/kg reduce hypoxic brain damage.^{38,39} In one study using a hypoxic-ischemic injury model in newborn rats, 20 mg/kg/day of caffeine for three doses resulted in a decrease in apoptosis of neuronal cells in the hippocampus and parietal cortex compared to controls.³⁹ A second study using a similar model found that a theophylline dose of 20 mg/kg prior to injury resulted in reduced brain injury compared to higher doses or controls.³⁸ Furthermore, the FDA caffeine label for apnea of prematurity trial recommends a loading dose of 20 mg/kg followed by a daily maintenance dose of 5 mg/kg. The higher maintenance doses in cohort 2 of our study is consistent with the dosing range we use to treat apnea of prematurity at UNC, and is also consistent with doses used in a large caffeine trial.⁴¹

4.4 End of Study Definition

A participant is considered to have completed the study if he or she has completed all phases of the study including the neurodevelopmental follow-up visit at 18-24 months, listed as the final study assessment in the Schedule of Activities (SoA), Section 1.3.

5 STUDY POPULATION

5.1 Inclusion Criteria

1. Documented informed consent from parent or guardian
2. \geq 36 weeks gestational age at birth
3. Receiving therapeutic hypothermia for a diagnosis of HIE
4. Intravenous (IV) access
5. Postnatal age $<$ 24 hours

5.2 Exclusion Criteria

1. Receiving $>$ 1 anti-epileptic drug for seizures
2. Sustained (>4 hours) heart rate $>$ 180 beats per minute
3. Known major congenital anomaly
4. Any condition which would make the participant, in the opinion of the investigator, unsuitable for the study

5.3 Lifestyle Considerations

Not applicable.

5.4 Screen Failures

Not applicable.

5.5 Strategies for Recruitment and Retention

We anticipate that 18 neonates will be recruited from up to 3 US NICUs, including the University of North Carolina at Chapel Hill (UNC) Newborn Critical Care Center (NCCC). Enrollment will begin at UNC and expand to other sites, if needed. The decision to provide therapeutic hypothermia will be at the discretion of the clinician. A neonate will be eligible for screening and enrollment in this study as soon as the decision is made by the clinician to provide therapeutic hypothermia for HIE. The parents of neonates undergoing therapeutic hypothermia will be approached for enrollment by study coordinators in a timely fashion to ensure that the first dose of study drug is given prior to 24 hours postnatal age. For neonates enrolled in the study, retention of subjects will be enhanced by close follow-up in the Special Infant Care Clinic, which is the standard of care for all neonates undergoing therapeutic hypothermia for HIE at UNC, or equivalent follow-up clinic at other sites.

6 STUDY INTERVENTION

6.1 Study Intervention(s) Administration

6.1.1 Study Intervention Description

The study drug is caffeine citrate injection for intravenous administration, which is commercially available and labelled by the FDA for the short term treatment of apnea of prematurity in neonates between 28 and <33 weeks gestational age.⁵¹

6.1.2 Dosing and Administration

Table 3. N and dosing scheme			
	N	Caffeine Loading Dose	Caffeine Maintenance Dose
Cohort 1	9	20 mg/kg IV prior to 24 hours postnatal age	5 mg/kg IV q24 hours x 2 doses (first dose 24 hours after loading dose)
Cohort 2	9	20 mg/kg IV prior to 24 hours postnatal age	10 mg/kg IV q24 hours x 2 doses (first dose 24 hours after loading dose)

The first 9 participants will be enrolled in cohort 1 and receive the doses as described in **Table 3**. All doses will be intravenous as the presence of a peripheral or central venous catheter is standard of care for neonates undergoing therapeutic hypothermia. Caffeine loading doses will be administered over 30 minutes and maintenance doses will be administered over 15 minutes via an infusion pump, followed by a normal saline flush administered over 5 minutes via an infusion pump.

6.2 Preparation/Handling/Storage/Accountability

6.2.1 Acquisition and Accountability

Detailed information will be part of the MOP.

6.2.2 Formulation, Appearance, Packaging, and Labeling

The study drug (caffeine citrate) is the commercially available intravenous formulation. This protocol will not specify the brand of product. Detailed information will be part of the MOP.

6.2.3 Product Storage and Stability

Detailed information will be part of the MOP.

6.2.4 Preparation

The pharmacy at each site will prepare and distribute the study drug and the drug will be administered by the bedside nurse.

6.3 Measures to Minimize Bias: Randomization and Blinding

Not applicable.

6.4 Study Intervention Compliance

Adherence to the protocol will be assessed by use of a participant drug log to be completed by the bedside nurse at the time of drug administration. We will record exact start and stop times of caffeine dose over the IV pump, as well as start and stop time of flush.

6.5 Concomitant Therapy

All drug and/or treatments are permitted while on study. All concomitant medications and treatments will be reported during the study drug administration period.

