1.2 Schema

1.3 Schedule of Activities (SoA)

	Screen/ Baseline	Treatment	Follow-up Period	Discharge/Transfer /Death	Final study assessment
Time point	< 24 hours postnatal age	Study day 1-3	7 days following last caffeine dose		18-24 Months
Informed consent	X				
Demographics	X				
Neurological Exam	X			X	X
Weight	X	X	X	X	X
Medical history	X				X ¹
Respiratory Support	X ²	X ²	X ²	X	
Laboratory evaluations ³	X	X	X		
Urine output	X	X	X		
Caffeine administration ⁴		X			
Concomitant medications		X	X		
Adverse events ⁵		X	X		
PK sampling ⁶		X	X		
Epigenetic sampling ⁷		X	X		
Clinical events of interest ⁸		X	X		
Head imaging ⁹		X	X	X	
Hearing screen				X	
Surgical procedures		X	X	X	
Bayley-III composite scores and GMFCS					X

¹ Follow-up visit will include information on hearing impairment requiring hearing aids, blindness, and cerebral palsy diagnosis. ² Highest respiratory support (room air, oxyhood, nasal cannula/CPAP, or mechanical ventilation) and maximum FIO₂ exposure during each 24-hour period. ³ See Section 8.2.1. ⁴ Includes exact start, stop, and flush times for all caffeine doses. ⁵ Seizures requiring > 1 anti-epileptic drug and necrotizing enterocolitis are adverse events of special interest. ⁶ Date and time for each sample. ⁷ Obtained from scavenged blood samples, if available. ⁸ Includes death, sepsis, disseminated intravascular coagulopathy, hypotension, hypertension, hepatic dysfunction, acute kidney injury, persistent pulmonary hypertension, and thrombocytopenia. ⁹ Includes cranial ultrasounds and head CT, if done per standard of care, and brain MRI.

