8 STUDY ASSESSMENTS AND PROCEDURES

8.1 Study Procedures

8.1.1 Screening/Baseline

Research staff will screen for eligibility requirements. After the parent or guardian has provided informed consent and after it has been determined that the participant satisfies all inclusion and no exclusion criteria, the following evaluations will be recorded in the CRF:

1. Participant demographics
 - a. Maternal race/ethnicity
 - b. Maternal age
 - c. Inborn/outborn
 - d. Infant sex
 - e. Gestational age (weeks)
 - f. Postnatal age (hours)
2. Neurological exam
 - a. Level of consciousness
 - i. Hyperalert or irritable
 - ii. Lethargic or poorly responsive
 - iii. Minimal or no responsiveness
 - b. Spontaneous activity
 - i. Slightly decreased
 - ii. Decreased
 - iii. Absent
 - c. Posture
 - i. Mild distal flexion
 - ii. Distal flexion, complete extension
 - iii. Decerebrate
 - d. Tone
 - i. Hypertonic
 - ii. Hypotonic
 - iii. Flaccid
 - e. Primitive Reflexes
 - i. Suck
 1. Normal
 2. Weak or bite
 3. Absent
 4. Unable to assess
 - ii. Moro
 1. Low threshold to elicit
 2. Weak or incomplete
 3. Absent
 4. Unable to assess
 - f. Autonomic

- i. Pupils
 - 1. Equal and reactive
 - 2. Constricted
 - 3. Dilated and either fixed or sluggishly reactive; asymmetric
 - 4. Unable to assess
- ii. Respiration
 - 1. Normal
 - 2. Periodic breathing
 - 3. Intubated or ventilated
- 3. Birth weight (grams)
- 4. Medical history
 - a. All Apgar scores (0-10)
 - b. Chest compressions in the delivery room (yes/no)
 - c. Lowest pH among cord arterial, cord venous, and arterial blood gas taken before 1 hour of age
 - d. Sentinel event, defined as placental abruption, shoulder dystocia, uterine rupture, or prolapsed cord
 - e. Severity of encephalopathy based on Sarnat staging³ (mild, moderate, or severe)
 - f. Start time of therapeutic hypothermia
- 5. Respiratory support at time of enrollment (room air, oxyhood, nasal cannula/CPAP, or mechanical ventilation) and maximum FIO₂ exposure during each 24-hour period
- 6. Concomitant medications (see Section 6.5)
- 7. Laboratory evaluations (see Section 8.2.1)

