8.3.4 Time Period and Frequency for Event Assessment and Follow-up

The occurrence of an adverse event (AE) or serious adverse event (SAE) may come to the attention of study personnel during the 7 day follow-up period.

All AEs including local and systemic reactions not meeting the criteria for SAEs will be captured on the appropriate case report form (CRF). Information to be collected includes event description, time of onset, clinician's assessment of severity, relationship to study product (assessed only by those with the training and authority to make a diagnosis), and time of resolution/stabilization of the event. All AEs occurring while on study must be documented appropriately regardless of relationship. All AEs will be followed to adequate resolution.

Any medical condition that is present at the time that the participant is screened will be considered as baseline and not reported as an AE. However, if the study participant's condition deteriorates at any time during the study, it will be recorded as an AE.

Changes in the severity of an AE will be documented to allow an assessment of the duration of the event at each level of severity to be performed. AEs characterized as intermittent require documentation of onset and duration of each episode.

The investigator will record all reportable events with start dates occurring any time after informed consent is obtained until time of discharge from the initial hospitalization.

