9.4.4.1 Clinical Definitions

1. Sepsis- Positive blood culture and ≥ 7 days of antibiotic treatment
2. Disseminated Intravascular Coagulopathy: Transfusion of platelets, fresh frozen plasma, or cryoprecipitate
3. Hypotension: Requiring inotrope or vasopressor support
4. Hypertension: Requiring antihypertensive medication
5. Hepatic dysfunction: AST > 200 IU/L or ALT > 100 IU/L
6. Acute Kidney Injury (AKI), stage 1-3 classified using Kidney Disease: Improving Global Outcomes (KDIGO) system (**Table 5**). We will use the highest serum creatinine per 24-hour period. A participant will be assigned a stage if they meet either serum creatinine or urine output criteria listed below.

Table 5. AKI KDIGO Classification⁶¹

Stage	Serum Creatinine (SCr)	Urine Output
0	No change in SCr or rise <0.3 mg/dL	≥ 1.0 mL/kg/hour
1	SCr rise ≥ 0.3 mg/dL within 48 hours or SCr rise ≥ 1.5 - $1.9 \times$ reference SCr ^a within 7 days	> 0.5 and ≤ 1 mL/kg/hour

2	SCr rise \geq 2.0-2.9 X reference SCr ^a	> 0.3 and \leq 0.5 mL/kg/hour
3	SCr rise \geq 3 X reference SCr ^a or SCr \geq 2.5 mg/dL or receipt of dialysis	\leq 0.3 mL/kg/hour

^aReference SCr will be defined as the lowest previous SCr value

7. **Persistent Pulmonary Hypertension**: Requiring inhaled nitric oxide and fraction of inspired oxygen >0.50
8. **Thrombocytopenia**: Platelet count $< 100,000$ per μL
9. **Seizures** will be defined by the receipt of > 1 AED, as we are interested in identifying seizures which are difficult to control.
10. **Necrotizing Enterocolitis** - Bell Stage II or III⁵⁷

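### The medication-recording windows conflict and clinical events of interest have no baseline entry, so treatment-defined events already present before the loading dose are not separated from those arising after caffeine

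*Combined protocol and SAP*

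**What the plan says.** **Medication record.** Section 6.5: "All concomitant medications and treatments will be reported during the study drug administration period". Section 4.1 says "the intervention duration will be 48 hours". In the Section 1.3 schedule, the row "Concomitant medications" is marked for treatment and for the follow-up period, but not for screening/baseline or discharge. Section 8.1.1 does list it at baseline, in an item that begins "6. Concomitant medications (see Section 6.5". Sections 8.1.2 and 8.1.3 list it for treatment and for the 7 days after the last dose, with the same pointer to 6.5.

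**Event definitions.** Section 9.4.4.1 defines several events by the treatment given. One entry reads "Hypotension: Requiring inotrope or vasopressor support", and sepsis is "Positive blood culture and ≥ 7 days of antibiotic treatment". Hypertension rests on antihypertensive medication, DIC on transfusion of blood products, and PPHN on inhaled nitric oxide together with an oxygen threshold. Seizures are defined by receipt of more than one anti-epileptic drug (AED).

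**Event record.** Clinical events of interest are marked in 1.3, and listed in 8.1.2 and 8.1.3, for treatment and follow-up only. Section 8.3.4 has AEs recorded from consent "until time of discharge from the initial hospitalization", with time of onset. It treats a condition present at screening as baseline and not as an AE.

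**The concern.** In a single-arm study of infants who are already ill from a perinatal insult, the safety summary must distinguish what was present before the drug from what appeared or worsened after it. For a laboratory-defined event such as hepatic dysfunction or thrombocytopenia, the schedule supplies baseline laboratory values. For a treatment-defined event, the counterpart is the treatment record before the first dose, and this is where the sections disagree. If 6.5 or 1.3 is followed, there is no baseline medication record. If 8.1.1 is followed, there is one, but no section asks for the start and stop times of these treatments.

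At stake is how the summary is read. An infant on a vasopressor before the loading dose and an infant who first needs one afterwards would both appear as hypotension in the treatment period. The independent safety monitor's review before cohort 2 and the final safety tables would both carry this mixture.

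**Working it through.** The plan states no figure on this point, so the check sets the sections side by side and then does simple window arithmetic.

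| Place | Baseline | Dosing | 7 days after last dose | Then to discharge |
|---|---|---|---|---|
| 6.5, medications | no | yes | no | no |
| 1.3, medications | blank | yes | yes | blank |
| 8.1.1 to 8.1.3, medications (each citing 6.5) | yes | yes | yes | not listed in 8.1.4 |
| 1.3 and 8.1.1 to 8.1.3, clinical events of interest | none | yes | yes | none |
| 8.3.4, AEs | from consent | yes | yes | yes |

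**Window lengths**
- Dosing: three doses 24 h apart = 48 h = 2 days.
- Dosing plus follow-up: 2 + 7 = 9 days from the loading dose.
- Pre-dose interval: up to 24 h, because Table 3 allows the loading dose at any time before 24 hours of age.
- Tail with no medication record under any section, taking the caffeine group's stay in Table 2 (median 19 days, IQR 16 to 32) and assuming loading at the end of day 1: 19 − 1 − 9 = 9 days at the median; 16 − 1 − 9 = 6 and 32 − 1 − 9 = 22 at the quartiles. This is the length of a gap in the log. It is not a rate of lost events.

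**Which events are affected.** The treatment-period list has nine clinical events of interest. Hypotension, hypertension and DIC are defined entirely by treatment; sepsis and PPHN in part. That is 5 of 9.

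**Does another rule separate pre-dose from post-dose?**
1. The 8.3.4 baseline rule applies to AEs. Clinical events of interest are a separate schedule row and a separate item in 8.1.2 and 8.1.3, and no section extends the rule to them.
2. The rule is anchored to screening. A treatment started between screening and the loading dose falls outside it.
3. Section 8.1.2 makes the day of the first dose study day 1. A treatment running earlier that day can therefore sit in the treatment column.
4. Sections 8.1.2 and 8.1.3 ask for date and time of caffeine doses (8.1.2) and of PK and epigenetic samples, but not of clinical events of interest.

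**Size.** The documents do not say how many infants are on these treatments before loading, so this must be assumed. With k such infants, the share attributable to the pre-dose state is k/9 in a cohort and k/18 overall:
- k = 1: 1/9 = 11.1 points; 1/18 = 5.6 points
- k = 2: 2/9 = 22.2 points; 2/18 = 11.1 points
- k = 3: 3/9 = 33.3 points; 3/18 = 16.7 points

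**The case against.** The best defence is that no section says events are derived from the medication log. Clinical events of interest and seizures requiring more than one AED are their own case report form items in treatment and follow-up. AEs carry onset and resolution times and run to discharge. Cultures and daily maximum inspired oxygen are recorded separately. All of this stands, and it rules out several stronger readings.

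- A reader might infer that events are missed once the log stops. The documents do not support this. A qualifying event after the 7-day period is still reportable as an AE to discharge; what is lost is the means to check it against dated treatment.
- A reader might infer that sepsis can never be identified, because a 7-day antibiotic course cannot fit in a 48-hour log. That would follow only if sepsis were ascertained from that log alone, and it is a listed event in its own right. The length of course required is a chosen definition, separate from the recording window.
- A reader might infer that pre-caffeine seizures are counted against caffeine. Section 5.2 excludes infants on more than one AED, so the definition is not met at entry, and 9.4.4 limits the exposure correlation to seizures after the first dose. A residual need for AED start times remains: a second drug begun between screening and loading, or a first drug begun before caffeine and a second after.
- A reader might infer that the cohort 2 decision is compromised. The only numeric trigger in 9.4.4 and 10.1.6 is more than one drug-related serious AE, which rests on causality assessment and not on counts of these events.

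The defence does not reach the missing baseline entry for clinical events of interest, nor the conflict between 6.5, 1.3 and 8.1.1 to 8.1.3. The case report forms and manual of procedures may hold dates that resolve part of this, but the protocol text does not require them.

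**Conclusion.** The point holds as one of attribution and verification. The sections give three medication windows: 2 days; 9 days without baseline; and baseline plus 9 days. None matches AE reporting to discharge. Five of nine clinical events of interest depend at least partly on treatment received, have no baseline entry, and are not covered by the AE baseline rule. As written, treatment running before the loading dose is not distinguished from treatment started after it.

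The size in practice is unknown, because the documents give no frequency of pre-dose treatment. What can be said is the weight of each misplaced infant: 11.1 points in a cohort, 5.6 points overall. The conclusion assumes that the forms follow the protocol text. It does not show that any event goes unrecorded, and the log's length relative to hospital stay should not be read as a miss rate. The correction is worthwhile because it is cheap and because a single-arm safety summary has no concurrent control to absorb the mixture.

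**What to change.** 1. Reconcile 6.5 and 1.3 with 8.1.1 to 8.1.3 so that one medication window applies throughout.
2. In 1.3 and 8.1.1, provide a baseline entry for both concomitant medications and clinical events of interest.
3. For the event-defining treatments only (AEDs, inotropes/vasopressors, antihypertensives, inhaled nitric oxide, antibiotics, blood products), record start and stop times from baseline to discharge, to match the AE window.
4. In 9.4.4, state that each clinical event will be reported as present before the first dose or as new/worsened after it, alongside the all-infant count.

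The event definitions, including sepsis, need not change. The cost is protocol and form wording plus slightly more chart abstraction for 18 infants.

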6.5.1 Rescue Medicine

Not applicable.

7 STUDY INTERVENTION DISCONTINUATION AND PARTICIPANT DISCONTINUATION/WITHDRAWAL

7.1 Discontinuation of Study Intervention

Participants may be withdrawn from the study at any time. Participants withdrawn from the study due to an AE, whether serious or non-serious, must be followed by the investigator until the clinical outcome from the AE is determined. Any participant who experiences an AE may be withdrawn at any time from the study at the discretion of the investigator. The AE(s) should be noted on the appropriate case report forms (CRFs), and the participant's progress should be followed until the AE is resolved or considered stable. If the AE may relate to overdose of study treatment, the package insert should be consulted for details of any specific actions to be taken.

Discontinuation from caffeine does not mean discontinuation from the study, and remaining study procedures should be completed as indicated by the study protocol. If a clinically significant finding is identified (including, but not limited to changes from baseline) after enrollment, the investigator or qualified designee will determine if any change in participant management is needed. Any new clinically relevant finding will be reported as an AE.

